8.9 Known drug reactions and interaction with other therapies

The most commonly reported adverse reactions in clinical trials for participants with severe refractory eosinophilic asthma included headache ($\geq 1/10$), injection site reactions ($\geq 1/1000$) and back pain ($\geq 1/1000$) (Pavord et al. 2017). The most common manifestation reported with local injection site reactions included pain, erythema, swelling, itching and burning sensation. For the full list of undesirable effects please refer to section 4.8 of the approved version of the Summary of Product Characteristics (SmPC) for Mepolizumab provided in the Investigator Site Files (ISF).

8.10 Concomitant medication

No interaction studies have been performed and there are no noted contraindications. Due to the mechanism of action of Mepolizumab, the potential of drug-drug interactions is considered to be low. Therefore, there are no restrictions on concomitant use of other medications. Patients will continue to receive all their normal medication for other conditions as clinically indicated and prescribed by their physician unless otherwise clinically indicated. Changes to baseline concomitant medication will be assessed at every trial visit and recorded in the Case Report Form (CRF).

8.11 Trial restrictions

Immediate (within hours of administration) and delayed (typically within several days) acute and delayed systemic reactions have been observed following administration of Mepolizumab. This includes hypersensitivity reactions (e.g. anaphylaxis, urticaria, angioedema, rash, bronchospasm, and hypotension).

Patients with pre-existing helminth infections should have been treated before entering the trial. If a participant becomes infected with a helminth infection and do not respond to anti-helminth treatment, temporary discontinuation of trial treatment should be considered. As helminth infections are very rarely seen in the UK, this is not expected to occur in this trial.

There is limited data on from the use of Mepolizumab in pregnant women. Animal studies have shown the drug to cross the placental barrier, though the potential to a human foetus is unknown. As a precautionary measure women of child-bearing potential (WOCBP) will receive a pregnancy test prior to trial treatment and must agree to use an acceptable method of birth control (see section 9.6 Pregnancy and pregnancy reporting) throughout the study duration. A urine pregnancy test will be undertaken prior to each subsequent administration of IMP following the baseline visit and at the final Visit 13/Final Follow-up.

In order to improve the traceability of biological medicinal products, the trade name and batch number of the administered product should be clearly noted in the accountability log seen only by members of the unblinded trial team.

8.12 Assessment of compliance with treatment

All doses of mepolizumab/placebo will be administered subcutaneously (SC) at the Respiratory BRC by an unblinded member of the study team. The prescribed dosage and mode of administration (see section 8.4 for dosage schedules) must not be altered. Injection time will be documented in the CRF. Any changes from the intended regimen must be recorded in the CRF.

See section 10 for a description of how non-compliance will be handled in the analysis.

8.13 Name and description of each Non-Investigational Medicinal Product (NIMP)

Sterile saline solution will be used for the placebo for those dosed before 01 March 2024; from 01 March 2024, a matched placebo in a pre-filled syringe will be used. Mepolizumab/placebo will be administered by an unblinded member of the study team so that the Investigator(s) and participants cannot distinguish Mepolizumab from placebo.

CONFIDENTIAL

9 PHARMACOVIGILANCE

9.1 Definitions

Term	Definition
Adverse Event (AE)	
Any untoward medical occurrence in a participant to whom a medicinal product has been administered, including occurrences which are not necessarily caused by or related to that product.
 
Clinical outcomes (e.g. moderate exacerbations not requiring hospitalisation) are exempt from adverse event recording and will be captured on the relevant case report form.

Adverse Reaction (AR)	
Any untoward and unintended response in a participant to an investigational medicinal product which is related to any dose administered to that participant.
 
The phrase "response to an investigational medicinal product" means that a causal relationship between a trial medication and an AE is at least a reasonable possibility, i.e. the relationship cannot be ruled out.
 
All cases judged by either the reporting medically qualified professional or the Sponsor as having a reasonable suspected causal relationship to the trial medication qualify as adverse reactions. It is important to note that this is entirely separate to the known side effects listed in the SmPC. It is specifically a temporal relationship between taking the drug, the half-life, and the time of the event or any valid alternative aetiology that would explain the event.

Serious Adverse Event (SAE)	
A serious adverse event is any untoward medical occurrence that:
 
 • results in death • is life-threatening • results in persistent or significant disability/incapacity • consists of a congenital anomaly or birth defect 
Other 'important medical events' may also be considered serious if they jeopardise the participant or require an intervention to prevent one of the above consequences.
 
NOTE: The term "life-threatening" in the definition of "serious" refers to an event in which the participant was at risk of death at the time of the event; it does not refer to an event which hypothetically might have caused death if it were more severe.
 
Clinical outcomes that require inpatient hospitalisation or prolongation of existing hospitalisation are exempt from serious adverse event reporting, unless the investigator deems the event to be related to the administration of the study drug. Clinical details about these outcomes will be routinely collected in the case report form.

Serious Adverse Reaction (SAR)	
An adverse reaction deemed to be serious (i.e. results in death, is life-threatening, results in persistent or significant disability/incapacity, consists of a congenital anomaly or birth defect.) and, in the opinion of the reporting Investigator, believed with reasonable probability to be due to one of the trial treatments, based on the information provided.

Suspected Unexpected Serious Adverse	
A serious adverse reaction, the nature and severity of which is not consistent with the information about the medicinal product in question set out in the reference safety information:

Reaction (SUSAR)	
 • in the case of a product with a marketing authorisation, this could be in the summary of product characteristics (SmPC) for that product, so long as it is being used within its licence. If it is being used off label an assessment of the SmPCs suitability will need to be undertaken. • in the case of any other investigational medicinal product, in the investigator's brochure (IB) relating to the trial in question
-------------------------	---

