3.2 Secondary Outcomes

3.2.1 Definition and Derivation of Secondary Outcomes

Exacerbations and Healthcare Utilisation

- Time from randomisation to next hospital readmission or death due to a respiratory cause

The time from randomisation to next hospital readmission or death (due to a respiratory cause) is defined as a time to event outcome measured in days. The date of randomisation as well as the date of readmission or death due to respiratory causes (whichever occurs first) will be used to calculate time to event. For participants not experiencing an event the time will be calculated from randomisation until last known follow-up assessment event-free. A variable to indicate event (with a value of 1) or no event (with a value of 0) will be derived. Details of the primary outcome analysis are included in section 5.5.

- Total number of hospital readmissions all cause up to 48 weeks

The total number of hospital readmissions (all cause) is defined as a count outcome. The number of hospital readmissions (all cause) in total during the 48 (truncated follow-up

minimum 24) weeks corresponding to each participant will be calculated. Where no hospital admission have occurred a value of zero will be derived.

- Total number of moderate exacerbations up to 48 weeks

The total number of moderate exacerbations is defined as a count outcome. The severity of a COPD exacerbation will be deemed as “Moderate” if the participant required treatment with steroids or antibiotics and was not hospitalised (Oba, Y. et al, 2017).

The number of moderate exacerbations each participant had over the course of 48 (truncated follow-up minimum 24) weeks will be calculated.

- Time from randomisation to treatment failure (defined as the composite of three endpoints: 1. treatment intensification with systemic corticosteroids and/or antibiotics for respiratory reasons; 2. step-up in hospital care for respiratory reasons including transfer to the intensive care unit or readmission; or 3. all-cause mortality)

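### Protocol 9.1 exempts moderate exacerbations from adverse event recording without the drug-relatedness exception it gives to hospitalised outcomes

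*Protocol*

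**What the plan says.** Protocol 9.1 holds two exemptions and one definition that bear on this point.

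- **AE row.** "Clinical outcomes (e.g. moderate exacerbations not requiring hospitalisation) are exempt from adverse event recording"; they go on an outcome form instead. The sentence does not mention relatedness.
- **SAE row.** Clinical outcomes that need or prolong an inpatient stay "are exempt from serious adverse event reporting, unless the investigator deems the event to be related to the administration of the study drug".
- **AR row.** The causal link is described as one where "a causal relationship between a trial medication and an AE is at least a reasonable possibility". The row then says that all cases judged by the reporting professional or the sponsor as "having a reasonable suspected causal relationship to the trial medication qualify as adverse reactions".

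Elsewhere, Protocol 9.3 makes the investigator responsible for recording and reporting AEs and ARs as the protocol requires. Protocol 9.8 continues AR recording until four weeks after the last dose. Protocol 8.11 describes immediate and delayed systemic reactions to mepolizumab: "This includes hypersensitivity reactions (e.g. anaphylaxis, urticaria, angioedema, rash, bronchospasm, and hypotension". SAP 3.2.1 grades a COPD exacerbation as moderate "if the participant required treatment with steroids or antibiotics and was not hospitalised".

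**The concern.** The two exemptions do the same job, which is to keep expected disease outcomes from swamping the safety data. Only one has a way back for an event that the investigator attributes to the drug. The protocol gives no reason for the difference.

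It matters here because the disease outcome and a known type of drug reaction can look alike. Bronchospasm is a listed reaction and may be delayed by several days, when the participant may be at home. If such an event in a COPD patient is treated with a steroid course and classified as an exacerbation, the AE row sends it to the outcome form. What is at stake is the completeness of the relatedness data for mepolizumab, and of what the DSMC sees by arm during the trial.

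**Working it through.** The plan gives no figure on this point, so the check is a comparison of passages. The question is where a non-serious event goes once it has been classified as a moderate exacerbation and the investigator suspects the drug.

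| Step | Source | What it does with the event |
|---|---|---|
| 1. Recording | Protocol 9.1, AE row | Outcome form, not AE form; no exception |
| 2. Same question for an admitted participant | Protocol 9.1, SAE row | Exemption lifted if judged related |
| 3. Causality, by concept | Protocol 9.1, AR row, definition | Link is between the drug and an AE; this event was not recorded as one |
| 4. Causality, by result | Protocol 9.1, AR row, all judged cases | It is an AR if someone makes the judgement |
| 5. Who must ask | Protocol 9.2 and 9.3 | 9.2 lists causality as an item to collect for SAEs and SUSARs; 9.3 asks the investigator to check for AEs, assign causality, and record AEs and ARs as the protocol requires |
| 6. Duration | Protocol 9.8 | AR recording runs to four weeks after the last dose; no carve-out |
| 7. Final tables | SAP 7 and Appendix 1 | Relatedness is tabulated for AEs and SAEs |
| 8. DSMC | Protocol 10.6 | Reports cover AEs, SAEs, demographics and completeness; the arm-split output described is AE summaries and listings |
| 9. Efficacy | SAP 3.2.1 and 6.5.1.3 | Counted as a moderate exacerbation and compared by arm |

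Steps 4 and 6 say that the event must be recorded as an AR if it is judged related. Steps 1 and 3 keep it off the form to which that judgement is attached. Step 5 does not settle the matter, because the duty in 9.3 refers back to the protocol's own requirements, which include the exemption. An investigator who follows the AE row literally completes step 9 and nothing in steps 7 or 8. One who follows the AR row does both. The documents support either course, so this is a conflict to be reconciled.

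The route has two limits.

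- **Seriousness.** Life-threatening and other important medical events remain SAEs under 9.1 even without admission, so only non-serious events are affected.
- **Classification.** SAP 3.2.1 grades an event already judged to be a COPD exacerbation. A bronchospasm not so judged, or not treated with steroids or antibiotics, falls outside that definition and remains a recordable AE.

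One calculation helps in reading the optional table under the fix. With 12 doses over 48 weeks (336 days), the seven days after each dose cover 12 × 7 / 336 = 25% of follow-up. For the shortest truncated schedule, 6 doses over 24 weeks (168 days), the share is 6 × 7 / 168 = 25%. If doses are on schedule and onset is unrelated to dosing, about a quarter of exacerbations in either arm would fall in that window by chance. Timing alone therefore cannot identify a few true reactions, and only a difference between arms would be informative.

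**The case against.** The strongest reply is that the AE sentence is silent on relatedness and the AR row is not. Every case judged related is an AR, 9.3 and 9.8 require ARs to be recorded, and no passage tells an investigator who suspects the drug to reclassify the event as an exacerbation. Keeping efficacy outcomes off the AE form is also deliberate: the amendment history shows that version 6.0 clarified which events are clinical outcomes.

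Other safeguards exist. Protocol 2.1 commits to monitoring and analysing all potential anaphylaxis. AEs and concomitant medication are reviewed at every post-baseline visit (Protocol 7.7), so a steroid course should come to light. The investigator may stop treatment on safety grounds (Protocol 7.8). Moderate exacerbations are compared by randomised arm, so a material excess caused by the drug would count against mepolizumab.

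Most of this stands. A reader might infer that a drug-induced bronchospasm treated at home is never assessed or reported as an AR. The documents do not support that: the AR definition and the recording duties still apply, and many such events would not meet the SAP definition of a moderate exacerbation. Nor do they show that hypersensitivity is in fact under-reported, or that dosing continues without any safety review.

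The reply does not explain why the exception was needed for admitted participants and not for others, and it does not remove the conflict within 9.1.

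**Conclusion.** The asymmetry is real, and the AE exemption conflicts with the AR definition and with the duties in 9.3 and 9.8. The consequence is a possibility: a non-serious event, suspected to be drug-related and classified as a moderate exacerbation, could miss causality assessment and be absent from the AE and relatedness tables and from the DSMC's arm-split listings.

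The size cannot be estimated. The documents give neither a moderate exacerbation rate nor a proportion of exacerbations that might be drug-related. It is tempting to multiply an assumed rate by follow-up: 0.5 to 2 per participant-year × 238 × 48/52 gives about 110 to 439 events. That counts all moderate exacerbations and gives everyone full follow-up despite the truncated schedule, so it does not measure the problem. The affected subset is probably small.

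The conclusion assumes that the AE row is applied as written. The case report form is not among the documents, so it may already hold a relatedness item.

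**What to change.** 1. **Protocol 9.1, AE row.** Reconcile it with the SAE and AR rows by adding the sponsor's own exception: "unless the investigator deems the event to be related to the administration of the study drug".
2. **SAP 7.** State that moderate exacerbations judged related are included in the AE and relatedness tables and still count in the moderate exacerbation outcome, so the efficacy analysis is unchanged.
3. **Optional, if onset dates are held.** Tabulate by arm the moderate exacerbations starting within seven days after a dose, read against the 25% chance share. SAP 5.1 uses dosing dates, but the documents do not show that exacerbation onset dates are collected.

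The cost is one sentence in each document. The downside is that a few events appear in both the efficacy and the safety tables, which a footnote can explain. Timing limits the protocol change: the current version is dated 10 May 2024 and Protocol 8.1 has dosing running to June 2024, so it would affect little prospective recording. The SAP statement can still be made, because SAP 1 allows amendment until database lock.

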3.5 Table of endpoints/outcomes

Objectives	Outcome Measures	Timepoint(s) of evaluation of this outcome measure (if applicable)
Primary Objective	Time from randomisation to next hospital readmission or death (all cause)	Time to event between randomisation and first event, up to 48 weeks.
Secondary Objectives Exacerbation and healthcare usage	Time from randomisation to first hospital readmission or death (respiratory cause)	Time to event, up to 48 weeks.
	Total number of hospital readmissions (all cause)	48 weeks (minimum duration of trial treatment of 24 weeks)
	Total number of moderate exacerbations	48 weeks (minimum duration of trial treatment of 24 weeks)
	Time from randomisation to treatment failure	Time to event, up to 48 weeks.
	Time from randomisation to death (all cause)	Time to event, up to 48 weeks.
	Time from randomisation to death (respiratory cause)	Time to event, up to 48 weeks.
	Time from randomisation to first hospital readmission (all cause)	Time to event, up to 48 weeks.
	Time from randomisation to first hospital readmission (respiratory)	Time to event, up to 48 weeks.
	Time to discharge from randomisation	Time from randomisation to discharge, up to 48 weeks.
Quality of Life/Symptoms	Extended MRC dyspnoea score (eMRC)	Weeks 0, 4, 8, 12, 24, 36, 48* *See section 4.1 – Truncated follow-up; Patients randomised from July 2023 will receive minimum 24 weeks follow-up.
	St George's Respiratory Questionnaire (SGRQ)	
	COPD Assessment Tool (CAT)	
	Warwick-Edinburgh Mental wellbeing score (WEMWBS)	
	London Chest Activities of Daily Living Questionnaire (LCADL)	
Physiological Measures	Short physical performance battery (SPPB)	Weeks 0, 4, 8, 12, 24, 36, 48* *See section 4.1 – Truncated follow-up; Patients randomised from July 2023 will receive minimum 24 weeks follow-up.
	Handgrip Strength	

Inflammatory Markers	Serum eosinophil count	Weeks 0, 4, 8, 12, 24, 36, 48*
	Sputum eosinophil count	*See section 4.1 – Truncated follow-up; Patients randomised from July 2023 will receive minimum 24 weeks follow-up.
Safety and Tolerability	AE event rate per year in the 48 weeks of the trial from first dose	48 weeks*
	SAE event rate per year in the 48 weeks of the trial from first dose	*See section 4.1 – Truncated follow-up; Patients randomised from July 2023 will receive minimum 24 weeks follow-up.
	Clinical assessments and investigations	

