The sputum eosinophil count (percentage) is defined as a continuous outcome that is expressed as a percentage (Belda, J. et al, 2000). Values are rounded to one decimal place.

Safety and Tolerability (all visits)

- AE event rate per year in the 48 weeks of the trial from first dose
- SAE event rate per year in the 48 weeks of the trial from first dose

The number of adverse and serious adverse events is defined as a count variable. Furthermore, AE and SAE event rates will be reported as incidence rates per person years and calculated as (total number of events / sum of all follow-up times) *52 where;

-Total number of events is a count of all AE/SAEs observed.

-Follow-up time is calculated per participant from time of first dose until the last trial assessment is recorded.

- Clinical assessments and investigations (heart rate, blood pressure, temperature)

Heart rate, blood pressure and temperature are defined as continuous outcomes that are measured in bpm, mmHg and °C, respectively. Temperature values are rounded to one decimal place.

Exploratory Outcome Measures

- Physical Activity using accelerometry (Weeks 0, 4, 8, 12, 24, 36, 48*)

The analysis of physical activity accelerometer data from GeneActive will be treated as an exploratory analysis and will be conducted independently outside the scope of this Statistical Analysis Plan (SAP).

*See section 1.2 – Truncated follow-up; Participants randomised from June 2023 will receive minimum 24 weeks follow-up.

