6.8 Changes to the Planned Analysis

None.

7 Safety and Adverse events

All safety data will be presented according to the Safety population.

All adverse events will be listed including characteristics such as seriousness, duration, relatedness, severity, action taken and outcome.

Adverse events' frequencies by seriousness, relatedness and severity will be summarised by treatment group and overall.

Adverse events frequencies will also be presented by treatment arm for each MedDRA Coding system organ class observed.

Graphical illustrations of frequencies by arm in total and by system organ class will be presented.

Furthermore, AE and SAE event rates will be reported as incidence rates per person years and calculated as (total number of events / sum of all follow-up times) *52 where;

- Total number of events is a count of all AE/SAEs observed.

- Follow-up time is calculated per participant from time of first dose until the last trial assessment is recorded.

8 References

Dodd, J. W., Hogg, L., Nolan, J., Jefford, H., Grant, A., Lord, V., ... Hopkinson, N. S. (2011). The COPD Assessment Test (CAT) - Response To Pulmonary Rehabilitation. A Multicentre, Prospective Study. *Thorax*, 66, 425–429.

Muller, J. P., Gonçalves, P. A., Fontoura, F. F., Mattiello, R., & Florian, J. (2013). Applicability of the London Chest Activity of Daily Living scale in patients on the waiting list for lung transplantation. *Jornal brasileiro de pneumologia : publicacao oficial da Sociedade Brasileira de Pneumologia e Tisiologia*, 39(1), 92–97.

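### An admission that meets no other seriousness criterion becomes an SAE only if judged drug-related, so the hospitalisation part of the by-arm SAE rate is selected on causality and the SAP does not account for it

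*Protocol*

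**What the plan says.** Protocol 9.1 lists death, threat to life, disability and congenital anomaly as making an event serious. It adds a discretionary route: "Other 'important medical events' may also be considered serious if they jeopardise the participant". Hospitalisation is not on the list. Instead, clinical outcomes that lead to an admission or a longer stay "are exempt from serious adverse event reporting, unless the investigator deems the event to be related to the administration of the study drug". The exempt admissions are not lost: "Clinical details about these outcomes will be routinely collected in the case report form". The SAR definition that follows repeats the seriousness list, again without hospitalisation. Protocol 9.4 puts deaths on the SAE reporting timeline whatever the cause.

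The SAE rate is a listed outcome. Protocol 3.5 gives it as "SAE event rate per year in the 48 weeks of the trial from first dose". SAP 3.2.1 defines the numerator, and SAP 7 repeats it: "Total number of events is a count of all AE/SAEs observed". SAP 7 adds that adverse event "frequencies by seriousness, relatedness and severity will be summarised by treatment group and overall", and that frequencies will be shown by arm and system organ class. Neither SAP section mentions the exemption.

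The primary outcome is all-cause readmission or death. All-cause readmission is also a time-to-event and a count secondary outcome. The only cause split among the readmission outcomes is respiratory against all-cause (Protocol 3.3).

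**The concern.** An exemption of this kind is reasonable for expedited reporting, where the trial expects many admissions. The difficulty comes when the same set of reported SAEs becomes the numerator of an outcome compared between arms. For an admission with no other seriousness criterion, the investigator's causality judgement decides whether it is counted at all. Such an event can enter as related but never as not related.

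Two things are at stake. First, the hospitalisation part of the SAE rate measures how often investigators suspect the drug, not how often participants were admitted, and nothing in the SAP tells the reader so. Second, a cardiac or infective admission that is not judged related and meets no other criterion may not appear in any system organ class table. The readmission outcomes would count it only as an admission that is not respiratory. Protocol 2.1 says that potential major adverse cardiac events will be monitored and analysed, but the SAP specifies no such analysis.

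**Working it through.** **1. Inputs.** From Protocol 10.1: 65% of placebo participants with an event by 48 weeks, hazard ratio 0.6, 226 participants (113 per group) before and 238 after 5% drop-out, where drop-out means recruited but never dosed. Also from 10.1: 64% readmitted at 12 months and 6% dead without readmission. From Protocol 9.4: mortality of 12% after severe exacerbations. The documents give neither an expected SAE rate nor the share of admissions judged related. That share is assumed here to lie between 1% and 10%.

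**2. The plan's own figure.** Mepolizumab event probability = 1 − 0.35^0.6 = 0.467. Mean over arms = (0.65 + 0.467)/2 = 0.559. Freedman's formula gives (1.960 + 0.842)² × (1.6/0.4)² = 125.6, so 126 events. 126/0.559 = 225.5, so 226. 226/0.95 = 237.9, so 238. Both stated figures reproduce.

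**3. Base.** The SAE rate runs from first dose in the safety population, so 113 per arm is the right base. Share of first events that are readmissions = 64/(64 + 6) = 0.914.

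- Placebo: 113 × 0.65 × 0.914 = 67.2
- Mepolizumab: 113 × 0.467 × 0.914 = 48.3
- Total 115.4; ratio 48.3/67.2 = 0.72

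These are first readmissions only; repeat admissions would add to them.

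**4. Equal share judged related in both arms** (Poisson counts, hospitalisation route only):

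| Share judged related | Placebo | Mepolizumab | Total | Chance mepolizumab shows more |
|---|---|---|---|---|
| 1% | 0.7 | 0.5 | 1.2 | 23% |
| 2% | 1.3 | 1.0 | 2.3 | 27% |
| 5% | 3.4 | 2.4 | 5.8 | 27% |
| 10% | 6.7 | 4.8 | 11.5 | 24% |
| All admissions counted | 67.2 | 48.3 | 115.4 | 3.5% |

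The expected ratio is 0.72 in every row. The selection loses precision, and the direction shown becomes unreliable.

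**5. Unequal shares.** The component ratio passes 1 once the mepolizumab share exceeds the placebo share by a factor of 67.2/48.3 = 1.39. With an assumed 2% on placebo and 5% on mepolizumab, the counts are 1.3 and 2.4, a ratio of 1.8. That is a difference of about one event and leaves out every other SAE. Adding only deaths to that example, at 6% or 12% of 113 in the placebo arm (using these as on-trial rates is an assumption):

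- Mepolizumab deaths scaled by 0.72: (4.9 + 2.4)/(6.8 + 1.3) = 0.90 at 6%; (9.7 + 2.4)/(13.6 + 1.3) = 0.82 at 12%.
- Deaths equal in both arms: (6.8 + 2.4)/(6.8 + 1.3) = 1.13 at 6%; (13.6 + 2.4)/(13.6 + 1.3) = 1.07 at 12%.

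**6. Make-up of the SAE set.** Suppose deaths of 6% to 12% of 226 (13.6 to 27.1), none judged related, and no other SAEs. At 2% of admissions judged related, related events make up 2.3/29.4 = 7.8% to 2.3/15.9 = 14.5% of the SAE set. With all admissions counted the figure would be 1.6% to 1.8%. At 10%, it is 30% to 46% instead of 8% to 9%.

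**The case against.** Most of the case against a stronger claim stands.

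- A reader might infer that any hospitalisation is an SAE only if judged related. The documents do not support that. A fatal, life-threatening or disabling admission is serious whatever its cause, an important medical event may be, and deaths are reported. The text does leave open which rule prevails when a non-fatal life-threatening admission is also a clinical outcome.
- A reader might infer that the SAE rate will point the wrong way. It need not. Investigators and participants are blinded, and equal attribution preserves the expected ratio. Reversal needs chance on very few events, or unequal attribution from partial unblinding or genuine drug reactions; in the last case more related events on mepolizumab is correct signal. The 1.8 in step 5 is one component under an assumed split.
- A reader might look for an SAE-by-relatedness table. SAP Table 7 pools AEs and SAEs, with relatedness and seriousness as separate row blocks and no cross-tabulation. Only the line listing in SAP Appendix 2 carries both for each event.
- The claim that non-respiratory admissions appear nowhere by system organ class is not established. If the underlying diagnosis is still recorded as an AE, it is coded and tabulated. The undefined term leaves this open.
- Admissions are compared by arm, unselected by causality, in the primary and secondary outcomes, and Protocol 10.3 makes the safety summaries descriptive. No confirmatory inference rests on the SAE rate.

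What this does not answer is that a listed outcome has a numerator partly chosen by the causality judgement, and that the SAP neither says so nor offers an unselected safety view of admissions by cause.

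**Conclusion.** The point holds in a limited form. An admission that is treated as a clinical outcome and meets no other seriousness criterion enters the SAE set only through the relatedness judgement, and the SAP uses that set as an outcome numerator without qualification. This follows from the text and needs no assumed rate.

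Its size does depend on assumptions: about 1 to 12 of some 115 first readmissions would enter by this route if 1% to 10% are judged related, all of them labelled related. The harm is a small, selected and noisy count in a safety outcome. It is not a systematic reversal: the expected ratio is 0.72 under equal attribution, and even the assumed 2% against 5% split gives 0.82 to 1.13 once deaths are added. The primary analysis and the readmission outcomes are unaffected. The change is worth making because it is cheap and the SAE outcome is otherwise hard to interpret.

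**What to change.** In SAP 3.2.1 and 7:

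1. Report the SAE rate for events meeting a seriousness criterion other than hospitalisation, whatever the relatedness.
2. Show admissions judged related on a separate line, with all admissions as the denominator.
3. Add one safety-population table of all admissions and prolonged stays from the outcome CRF, by arm and by cause or system organ class, whatever the relatedness.
4. State the exemption in a footnote to the SAE outputs, and say which admissions the term *clinical outcomes* was taken to cover.

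In Protocol 9.1, reconcile the SAE definition with the SAR seriousness list. As written, an admission judged related is reportable as an SAE but does not by itself meet the SAR list. The exemption for expedited reporting can stay as it is.

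The cost is SAP wording, one table and some extra coding. Protocol 9.3 assigns MedDRA coding to AEs, SAEs and SARs only, so coding the remaining admissions is new work, although their clinical details are already collected.
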